7.3 LOST TO FOLLOW-UP

A participant will be considered lost to follow-up if he or she fails to return for three scheduled visits and is unable to be contacted by the study site staff.

The following actions must be taken if a participant fails to return to the clinic for a required study visit:

- The site will attempt to contact the participant and reschedule the missed visit within one week and counsel the participant on the importance of maintaining the assigned visit schedule and ascertain if the participant wishes to and/or should continue in the study.
- Before a participant is deemed lost to follow-up, the investigator or designee will make every effort to regain contact with the participant (where possible, 3 telephone calls and, if necessary, a certified letter to the participant's last known mailing address or local equivalent methods). These contact attempts should be documented in the participant's medical record or study file.
- Should the participant continue to be unreachable, he or she will be considered to have withdrawn from the study with a primary reason of lost to follow-up.

8 STUDY ASSESSMENTS AND PROCEDURES

8.1 EFFICACY ASSESSMENTS

Participants in this proposed study will provide the following efficacy data: (A) data from clinician-administered structured interviews (e.g., structured diagnostic interview with the SCID-5 and CAPS-5, clinical evaluation); (B) self-report data (e.g., symptom measures); and (C) behavioral data (online Extinction Learning Task). Additionally, participant will provide data on (D) demographics (e.g., age, sex, race, education, socioeconomic status); (E) measures of estimated IQ and cognitive functioning; and (F) psychiatric history and treatment, including any history of psychiatric hospitalization.

Diagnostic and Assessment Procedures: The diagnostic interviews and clinical ratings will be conducted by Master's- or PhD-level clinical raters well-trained in diagnostic interviews and the clinical rating scales, supervised by the PI. Bi-annual inter-rater reliability procedures are conducted at DAC to ensure adequate calibration of inter-rater reliability (ICC > 0.90). In the event of staff turnover, new raters must achieve this threshold of reliability prior to participation.

The **Structured Clinical Interview for DSM-5 (SCID-5)** is the most widely used structured diagnostic interview to determine psychiatric diagnoses in clinical research settings based on DSM-5 criteria. The SCID-5 is organized into diagnostic modules, to assess mood, psychotic, substance use, anxiety, obsessive-compulsive and related, eating, and trauma- and stressor-related disorders, and other disorders⁵¹. The SCID-5 will be used in this study to determine whether subjects meet DSM-5 criteria for PTSD and to assess other co-morbid psychiatric diagnoses, in order to determine study eligibility.

The **Clinician Administered PTSD Scale for DSM-5 (CAPS-5)** is a structured diagnostic interview and the gold standard for assessing the DSM-5 symptoms of PTSD. The scale also assesses social and occupational functioning, dissociation symptoms, and the validity of symptom reports. The CAPS-5 uses a single 5-point ordinal rating scale to measure symptom severity. Symptom severity ratings combine information about symptom frequency and intensity obtained by the interviewer. Psychometric properties indicate high criterion and construct validity and high agreement with a self-report measure of PTSD.⁵⁰ The CAPS-5 requires approximately 40 minutes to administer. The CAPS-5 will be administered at screening to determine PTSD symptom severity. In addition to meeting DSM-5 criteria for PTSD, subjects must also have a total CAPS-5 score ≥ 30 , indicating at least moderate PTSD symptom severity, in order to be eligible to participate in this study. The CAPS-5 will also be used to determine ketamine responder or non-responder status of participants following the first four ketamine infusions. Importantly, participants' total CAPS-5 severity scores will serve as the **primary outcome of interest**.

The **Montgomery-Asberg Depression Rating Scale (MADRS)** is a 10-item instrument used for the evaluation of depressive symptoms in adults and for the assessment of any changes to those symptoms.⁵² Each of the 10 items is rated on a scale of 0 to 6, with differing descriptors for each item. These individual item scores are added together to form a total score, which can range between 0 and 60 points. The estimated time to administer this scale is 20 minutes. Inter-rater reliability of the scale is high and scores correlate significantly with those of the HAM-D. On the infusion days a modified MADRS will be used that will exclude the sleep and appetite items. The MADRS will be used in this study as a secondary outcome measure, to assess change in co-morbid depressive symptom levels over time. Additionally, the MADRS will be employed to assess severity of co-morbid depressive symptoms as a clinical predictor for Aim 3 analyses.

The **Montreal Cognitive Assessment (MoCA)** is a widely used cognitive screening tool to differentiate mild cognitive impairment from cognitive changes associated with health aging.⁵⁵ A recommended cutoff score of 23 will be used to determine eligibility for this study, based on meta-analytic findings indicating that the cutoff of 26/30 originally suggested for this measure is associated with a higher percentage of false positives, especially among individuals of lower education or older age.⁷⁸

The **Wechsler Test of Adult Reading (WTAR)** is a neuropsychological assessment measure used to derive a pre-morbid estimate of intelligence, and requires participants to read a list of 50 words.⁵⁴ The WTAR will be administered at study screening to estimate participant IQ. Subjects with estimated IQ < 80 will

be excluded from the study. Additionally, estimated IQ derived with the WTAR, used in a prior non-inferiority RCT comparing WET to CPT,⁴¹ will be used as a predictor for Aim 3 analyses.

The **Childhood Trauma Questionnaire (CTQ)** is a widely used, valid and reliable retrospective self-report scale to screen for a history of childhood abuse and neglect. It includes a total of 28 items, and yields five subscale scores –emotional abuse and neglect, physical abuse and neglect, and sexual abuse–, as well as a minimization-denial score.⁵⁶ In the proposed study, the CTQ will be employed as a trauma history predictor for Aim 3 analyses.

The **Traumatic Life Events Questionnaire (TLEQ)** is a commonly used and rigorously tested self-report scale to assess the frequency, severity, and timing of a wide range of traumatic experiences experienced across the individual's lifetime, including childhood and adulthood.⁵⁷ Lifetime number of traumas, trauma type, and timing will be employed as trauma history predictors for Aim 3 analyses.

The **PTSD Checklist for DSM-5 (PCL-5)** is a widely used 20-item self-report measure to assess the 20 DSM-5 PTSD symptoms.⁵⁸ The PCL-5 measure has a Specific version to assess severity of PTSD symptoms in relation to a specific trauma. The Specific version of the PCL-5 will be used in this study as an additional, secondary outcome measure of PTSD symptom severity.

A 5-item abbreviated version of the **Medical Outcomes Study Social Support Survey (MOS-SSS)**,⁶⁸ a widely used self-report scale assessing perceived social support, including emotional/informational, tangible and affectionate support, utilizing a 5-point Likert scale. This scale will be administered at baseline (before the first infusion) and again 3 weeks after the addition of WET. This scale will be used for exploratory analyses for Aim 3.

The **Perceived Ability to Cope with Trauma (PACT)**⁷⁰ is a 20-item self-report scale assessing perceived coping abilities following a traumatic event. There are two main subscale scores: Forward-focused Coping score, reflecting the respondent's ability to maintain goals and plans following a traumatic event, and Trauma-focused Coping score, reflecting the respondent's ability to face feelings and cognitions relating to a traumatic event. Additionally, a Flexibility score can be calculated to determine the respondent's ability to engage in both forward-focused and trauma-focused coping strategies following a traumatic event. This scale will be administered at baseline (before the first infusion) and again 3 weeks after the addition of WET. This scale will be used for exploratory analyses for Aim 3.

The short-item **Centrality of Event Scale (CES)**⁶⁹ is a 7-item scale that measures how central the most stressful/traumatic event is to an individual's identity and life narrative. This scale will be administered at baseline (before the first infusion) and again 3 weeks after the addition of WET. This scale will be used for exploratory analyses for Aim 3.

The **Impact of Event Scale-Revised (IES-R)** is one of the most widely used self-report measures of stress reactions to traumatic events,⁶⁷ measuring both intrusion and avoidance. Correlations between IES-R subscales and PTSD diagnosis assessed with the CAPS are high (>0.75). Unlike the PCL-5, this scale is able to assess changes in PTSD symptoms (intrusion and avoidance) over a 24-hour time period. In this study, we will use this measure as a secondary outcome measure to assess for rapid improvement in PTSD symptom severity at 24-hours after the first ketamine infusion, and to assess symptom change at each ketamine infusion and on the ketamine response assessment day.

The **Quick Inventory of Depressive Symptomatology – Self-Report (QIDS-SR)** is a commonly used self-report scale to assess depressive symptom severity.⁶⁶ The total score of the QIDS-SR is based on the nine criterion symptom domains of major depressive disorder. In this study, we will use this measure as a secondary outcome measure to assess for rapid improvement in comorbid depressive symptom severity at 24-hours after the first ketamine infusion, and to assess symptom change at each ketamine infusion and on the ketamine response assessment day.

The **Hood Mysticism Scale (HMS)** is a validated measure of subjective spirituality, tested in multiple cultural contexts.⁷⁹ More recently this scale has been used to capture mystical or spiritual experiences during sub-anesthetic ketamine infusions, and there is evidence that these mystical experiences under ketamine treatment may mediate treatment response, at least in alcohol use disorder populations.⁸⁰ In this study, we will use the 8-item version of this scale to assess mystical experiences for exploratory analyses of mediators of response to ketamine. This scale is administered immediately after the end of Infusions 1 and 2, as we expect participants' experiences to be more intense during the first two infusion days.

The **Psychological Insight Questionnaire (PIQ)** assesses insightful experiences, which may be an essential part of psychedelic treatments.⁸¹ This newly developed questionnaire assess many aspects of psychological insight, including realizations about personality, relationships, emotions, and behaviors, with the goal of assessing these experiences in clinical trials of psychedelic medications. This scale will be administered at the end of the post-infusion monitoring period on Infusions 1 and 2, as we expect participants' experiences to be more intense during the first two infusion days.

The **Columbia Suicide Severity Rating Scale (C-SSRS)** is a comprehensive, semi-structured interview measure commonly employed in clinical trials. The C-SSRS measures the full spectrum of suicidality, including passive and active suicidal ideation, suicidal intent, and suicidal behaviors.⁶⁰ All study subjects will be assessed for suicidal ideation and behavior by the study PI or other trained member of the study team. Both past-month and lifetime versions of the C-SSRS will be administered at study screening. Individuals who score a 4 or greater on the past-month suicidal section, or who have engaged in any suicidal behavior in the past month, will be excluded and referred promptly for clinical care. Our clinicians and staff at the Depress Anxiety Center all undergo formal web-based training on administering the C-SSRS, and have extensive experience in its utilization. The Center has established SOPs for handling suicidality. For patients who do not show suicidality at the described threshold and proceed to participate in this study, the C-SSRS will be administered at each assessment time point (until 12 weeks, and then monthly up to 24 weeks or until loss of response), to assess for suicidal ideation and participant safety throughout the study. Participants with scores of 4 or greater at any point during the study will be exited from the study and promptly referred for clinical care.

The **Sheehan Disability Scale (SDS)** is a brief, 5-item self-report scale that assesses functional impairment in domains of work or school, social life, and family life.⁵⁹ Higher scores on this scale represent higher functional impairment. This scale will be administered at screening, and then at each assessment time point (weekly until 12 weeks, and then monthly up to 24 weeks or until loss of response).

The **Clinical Global Impression –Severity and –Improvement scales (CGI-S and CGI-I)** are among the most widely used brief assessment tools in psychiatry and clinical trials.⁸² The CGI-S will be administered

at screening and baseline prior to any infusions, and both the CGI-S and the CGI-I will be administered at each assessment time point (weekly until 12 weeks, and then monthly up to 24 weeks or until loss of response) by the PI or another study clinician, to determine global severity of psychiatric illness.

The **Brief Psychiatric Rating Scale (BPRS)** is a clinician-administered assessment used to capture acute behavioral changes throughout treatment.⁷³ We will use only the four items assessing positive (+) symptoms of psychosis such as conceptual disorganization, hallucinatory behavior, suspiciousness, and unusual thought content for this proposed study. The scale will be administered before and after each infusion.

The **Clinician-Administered Dissociative States Scale (CADSS)** is commonly used in ketamine studies, and will be administered before and after each infusion to assess the severity of dissociative symptoms associated with ketamine administration.⁷²

The **Young Mania Rating Scale (YMRS)**, first item (assessing elevated mood), is commonly used in ketamine studies.⁷⁴ We will administer only the first item of the YMRS before and after each infusion.

Online Extinction Learning Task: The computerized task, administered online, consists of three phases: an initial aversive conditioning phase (in context A), extinction learning phase (in context A), and further

[figure not shown]

Figure 7. Online extinction learning task (updated version). Participants are told that they are traveling through different zones of a spaceship, and needed to escape with enough space coins to power their journey home. Unfortunately, the coins need to be carried by helper robots, some of whom are unreliable. On each trial, participants encounter a robot and rate how likely they think that robot will be to lose coins using a sliding bar (participants are informed that their ratings will not change the outcome they observe, but that their predictions should be as accurate as possible in order to aid future space travelers). In a second version of the task (identical in structure but with an underwater setting), participants must travel through different parts of the ocean and predict how likely they think different sea creatures they encounter are to keep or lose pearls they must trade for their passage.³⁷

extinction learning (in novel context B) (see Figure 7). Importantly, the conditioned stimulus (CS) associated with the aversive loss outcome (US), the CS+, is only partially reinforced ($P(US|CS+)=1/3$), and the transition to extinction ($P(US|CS+)=0$) is unsignaled. This design maximizes uncertainty about whether CS+ trials during extinction should be grouped with unreinforced conditioning phase CS+ trials, implying a common cause is responsible for both kinds of observations, or instead that the change in contingencies indicates it is likely that a new cause is active in the environment. The predictive measure generated from this task for Aim 2 analyses (PTSD symptom change between baseline and 12 weeks from the start of WET) is the difference in discrimination between CS+ and CS- across the first six blocks of the task.

Further, loss expectancy ratings data from each trial of the online extinction task will be analyzed via a computational model of latent cause inference developed by Gershman, Niv, and colleagues^{75,76} (see Data Analysis Strategy). There are two versions of the task (see description in Figure 7 note): one version will be administered prior to any ketamine infusions, and the second version after completion of the first four infusions. We will examine whether improvement in extinction learning from baseline to completion of four initial ketamine infusions (prior to starting WET) is associated with PTSD symptom improvement from baseline to 12 weeks from the start of WET.

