Eligible patients will receive a total of 6 ketamine infusions and 5 WET sessions. The primary outcome will be change in PTSD symptom severity assessed by the Clinician-Administered PTSD Scale for DSM-5 (CAPS-5) from baseline (before the first infusion) to 12 weeks from the start of WET. All participants will be assessed until week 12 following the start of WET. They will complete weekly assessments from baseline until 6 weeks from the start of WET, as well as assessments at 12 weeks from the start of WET. At other time points between 6 and 12 weeks, participants will be assessed weekly, or less frequently as tolerated. Although initial response to ketamine (PTSD and co-morbid depressive symptom improvement) will be assessed after the first four infusions (prior to starting WET), all participants will receive 6 infusions and 5 WET sessions regardless of their initial response to ketamine. Participants will be asked not to make any changes to any concomitant treatment (i.e., medication dosages, psychotherapy) during this period.

Thereafter, participants who remain improved at the 12-week time point (compared to baseline) will then receive additional monthly assessments up to 24 weeks or until loss of this improvement.

We will also evaluate whether extinction learning ability –assessed with a computerized extinction learning task– is associated with PTSD symptom improvement from baseline to 12 weeks from the start of WET. If demonstrated to result in significant and maintained PTSD symptom improvement, this novel combined treatment may represent a promising intervention for individuals with chronic PTSD, deserving further study.

Objectives:

Primary Objective: To evaluate the efficacy of adding WET to ketamine therapy in improving PTSD symptoms from baseline to 12 weeks from the start of WET, in individuals with chronic PTSD .

Secondary Objectives (exploratory): (1) To evaluate improvement in PTSD symptoms from baseline to 6 weeks, and on other measures from baseline to 6 weeks, and from baseline to 12 weeks; (2) To evaluate durability of PTSD symptom improvement beyond 12 weeks in patients who remain improved, up to 24 weeks; (3) To evaluate whether ketamine-induced change in extinction learning is associated with improvement in PTSD symptoms from baseline to 12 weeks from the start of WET.

Endpoints:

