1.3 SCHEDULE OF ACTIVITIES (SOA)

Procedures	Screening	Baseline	Ketamine Infusions	24 hour Follow-Up Visit	Assessment of Response to Ketamine	WET Sessions	Weekly Assessment Until 12 weeks	Monthly Assessment Until Loss-of-Response
	Day - 28 to 0	Visit 1a, Day 1	Visit 1a-9; Days 1, 3, 5, 8, 11, 12	Visit 1b, Day 2	Visit 5, Day 9	Visit 6-12, Days 10, 12, 16, 18, 22	Visits 10, 13-23, Days 12, 19, 26...	Visits 23-26, Days 33...
Informed consent	x							
Demographics	x							
Medical history	x							
SCID-5	x							
CAPS-5	x	x			x		x	x
MADRS	x	x			x		x	x
WTAR	x							
MoCA	x							
IES-R		x	x	x	x			
QIDS-SR		x	x	x	x			
PCL-5	x	x			x		x	x
MOS-5		x					x ¹	
CES		x					x ¹	
PACT		x					x ¹	
CTQ	x							
TLEQ	x							
SDS	x	x		x	x		x	x
HMS			x ²					
PIQ			x ²					
C-SSRS	x	x			x		x	x
CADSS		x	x					
BPRS		x	x					
YMRS		x	x					
Extinction Learning Task	x				x			
CGI	x	x	x	x	x		x	x
Concomitant medication review	x	x	x	x	x		x	x
PRISE	x	x	x	x	x		x	x

Adverse event review and evaluation	x	x	x	x	x	x	x	x
Physical exam (including height and weight)	x							
Vital signs	x		x					
Weight	x		x					
EKG	x							
Routine labs	x							
Plasma ketamine and norketamine levels			x ³					
Urine pregnancy test	x		x					
Urine drug screen (UTOX)	x		x					
Ketamine infusion (0.5 mg/kg)			x					
Written Exposure Therapy (WET)						x		
Complete Case Report Forms (CRFs)	x	x	x	x	x	x	x	x

¹Visit 14 and 23 only

²only at Infusions 1 and 2

³only at Infusion 1

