All participants will be administered WET, beginning after they complete the first four infusions. WET will be delivered remotely by therapists to participants in their homes, via a HIPAA-compliant video telehealth platform, using methods implemented before the COVID-19 pandemic and further developed during the pandemic by study consultant [name], who co-developed the WET intervention.⁶⁵ Therapists will be Master's- or PhD-level mental health providers, supervised by [name]. WET will be delivered over a total of two weeks. The first two sessions of WET will be delivered starting after completion of the first four ketamine infusions, and interleaved with the last 2 ketamine infusions (each WET session and ketamine infusion occurring on one of four different days). The ketamine dose and administration protocol will be the same for all six infusions. The last three sessions of WET will be delivered the following week, after completion of the six ketamine infusions. Participant narratives will be collected as part of the WET sessions, as they are a necessary part of treatment and are used to ensure that the instructions for each writing session are followed by the participants. Collection will be completed securely, either by uploading a picture of the narratives to the REDCap database, uploading a scanned copy of the narratives, or by participants delivering the narratives in person (if there is a planned in-person visit shortly thereafter) or by mail.

e. Assessments and Outcome Measures (please see **3.1 Schedule of Activities** for additional details). Assessments will be administered weekly starting at baseline, prior to the first infusion.

Primary outcome measure: The Clinician-Administered PTSD Scale (CAPS-5),⁵⁰ the gold standard measure in clinical trials in individuals with PTSD, will be administered weekly by a blinded clinical rater. The primary outcome is change in PTSD symptom severity as measured by the CAPS between baseline and 12 weeks following the start of WET. All participants will be followed for 12 weeks. Participants who remain improved will additionally be followed monthly for 12 to 24 weeks.

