Secondary outcome measures (exploratory): The CAPS-5 will be administered weekly (beginning at baseline prior to the first ketamine infusion) until 6 weeks from the start of WET; thereafter, the CAPS-5 will be administered weekly as tolerated until 12 weeks; all participants will be administered the CAPS-5 at the 12-week time point. Participants who maintain PTSD symptom improvement after 12 weeks will be assessed monthly up to 24 weeks from the start of WET or until loss of improvement, by the blinded clinical rater. The PCL-5 and SDS (self-report scales), the MADRS (administered by the blinded clinical rater), and the CGI-S and CGI-Improvement scales (administered by a study psychiatrist or clinician) will be administered at the same time points until 12 weeks, and then monthly up to 24 weeks or until loss of improvement (See **3.1 Schedule of Activities**). The Quick Inventory of Depressive Symptomatology-Self-Report version (QIDS-SR)⁶⁶ and the Impact of Events Scale-Revised (IES-R),⁶⁷ both self-report scales, will be administered at baseline, 24 hours after the first infusion, at each infusion visit, and on the day of response to ketamine assessment, to capture any ketamine-related rapid changes in symptom levels. An abbreviated version of the Medical Outcomes Study Social Support Survey (MOS-SSS),⁶⁸ the Centrality of Event Scale (CES),⁶⁹ and the Perceived Ability to Cope with Trauma Scale (PACT)⁷⁰ will be administered at baseline (prior to any infusions) and again 3 weeks after the first WET session; data from these scales will be used for Aim-3 analyses.

Safety Assessments: Participants will be evaluated prior to each infusion by the PI or another study-affiliated psychiatrist; including review of vital signs, weight/BMI, drug and pregnancy tests, concomitant medications and adverse events. Participants will be monitored continuously during all ketamine infusions. On infusion days, side effects will be assessed with the Patient-Rated Inventory of Side Effects (PRISE) Adverse Event Visit Checklist,⁷¹ the Clinician-Administered Dissociative States Scale (CADSS),⁷² the Brief Psychiatric Rating Scale (BPRS) 4 items assessing positive symptoms,⁷³ and the Young Mania Rating Scale first item.⁷⁴

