9.4.9 EXPLORATORY ANALYSES

Secondary efficacy endpoint analyses and Aim 2 analyses are exploratory (see details above).

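### Section 8.1 shortens the MADRS on infusion days with no exception, and the baseline MADRS falls on the first infusion day, so read literally the MADRS change compares a short baseline with a full follow-up.

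*Combined protocol and SAP*

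**What the plan says.** Section 8.1 describes the MADRS as 10 items, each scored 0 to 6, with a total of 0 to 60. It then adds: "On the infusion days a modified MADRS will be used that will exclude the sleep and appetite items". It makes no exception for the baseline rating.

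The Schedule of Activities (1.3) places Baseline at Visit 1a, Day 1. The infusion column is headed "Visit 1a-9; Days 1, 3, 5, 8, 11, 12", so baseline and the first infusion share a visit and a day. The MADRS row is marked at screening, baseline, the response assessment (Day 9), the weekly visits and the monthly visits. It is blank under Ketamine Infusions and carries no footnote about form. The weekly column lists Day 12 first, and Day 12 is also an infusion day as printed.

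Several places put baseline ahead of treatment. The synopsis defines the primary outcome "from baseline (before the first infusion) to 12 weeks from the start of WET". Section 4.1 says "Assessments will be administered weekly starting at baseline, prior to the first infusion" and, for the CAPS-5, "The CAPS-5 will be administered weekly (beginning at baseline prior to the first ketamine infusion) until 6 weeks from the start of WET". The MADRS is among the scales that, per 4.1, "will be administered at the same time points until 12 weeks, and then monthly up to 24 weeks or until loss of improvement".

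The synopsis and Section 3 both make MADRS change from baseline to weeks 6 and 12 a secondary (exploratory) endpoint. The synopsis extends change on the other measures to weeks 16, 20 and 24 in participants who stay improved. Section 3 limits those later weeks to PTSD severity.

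**The concern.** Placing baseline before the first infusion does not move it to another day. A Day 1 pre-infusion rating is still a rating on an infusion day, so the sentence in 8.1 reaches it. The week 6 and week 12 ratings fall after the last infusion and would use the full form. The two ends of the change score would then rest on different sets of items.

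Dropping non-negative items at baseline only can lower the baseline but never raise it, so the error runs one way, toward less improvement. There is no control arm in which the same offset could cancel. The items not rated on Day 1 cannot be recovered later. No section exempts the baseline, names the screening MADRS as the baseline, or gives a rule for scoring common items.

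**Working it through.** **Inputs.** From 8.1: 10 items, 0 to 6 each, total 0 to 60; sleep and appetite items omitted on infusion days. From 1.3: infusion days 1, 3, 5, 8, 11, 12; MADRS at screening and on Days 1, 9, 12, 19, 26 and onward; first WET session on Day 10. *Assumption:* one sleep item and one appetite item are dropped. The documents do not give the number.

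**Plan's own figure.** 10 × 6 = 60, which reproduces the stated maximum. Under the assumption, the modified form has 8 items and a maximum of 8 × 6 = 48. The difference is 60 − 48 = 12.

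**Which ratings the rule reaches.** Infusion days {1, 3, 5, 8, 11, 12} intersected with MADRS days {1, 9, 12, 19, 26, …} gives {1, 12}. Day 9 (pre-WET) is not an infusion day. Weeks 6 and 12 from Day 10 are about Day 10 + 42 = 52 and Day 10 + 84 = 94, well past Day 12. Section 7.1 also collects symptom measures, with the MADRS as an example, when treatment is discontinued, and that visit could fall on an infusion day.

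**Effect on change from baseline.** Let B10 be the full baseline, B8 the shortened baseline, Sb the baseline score on the dropped items, and F10 the full follow-up. Then B10 = B8 + Sb, and

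F10 − B8 = (F10 − B10) + Sb, with 0 ≤ Sb ≤ 12.

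The recorded change is shifted by 0 to +12 points per participant, toward less improvement. The group mean change shifts by the group mean of Sb.

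**Illustration only.** The documents give no MADRS totals or item scores; Section 4.2 reports the earlier trial's MADRS result only as F, p and d = 0.92. If every item scored equally (a further assumption), Sb would be 0.2 × B10:

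| True baseline | Recorded | Improvement understated by |
|---|---|---|
| 10 | 8 | 2 |
| 20 | 16 | 4 |
| 30 | 24 | 6 |
| 40 | 32 | 8 |

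A true fall from 30 to 15 (−15) would be recorded as 24 to 15 (−9).

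**Other outputs.** The Day 1 to Day 9 step in the summaries, individual plots and any mixed models of 9.4.3 shifts by the same Sb. Change from pre-WET (9.4.1) to weeks 6 and 12 uses the full form at both ends, so its shift is 0. If Day 12 stands as printed, that one rating is lowered by its own dropped-item score relative to Days 9 and 19.

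**The case against.** The strongest reply is that the harmless reading is the natural one. The schedule separates Baseline from Ketamine Infusions although both include Day 1. It marks the MADRS under the first and leaves it blank under the second, whereas the IES-R, QIDS-SR, CADSS, BPRS and YMRS are marked under both. The score is described as 10 items, 0 to 60. On that reading the full form is given on Day 1 and the shift is 0. This stands as evidence of intent. It does not settle the matter, because the sentence in 8.1 is unqualified and nothing else assigns a form to Day 1.

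The reply also rules out some stronger readings that a reader might infer:

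- *That 1.3 contradicts 8.1 on the form.* It cannot, because it names no form. The mismatch appears only when the rule in 8.1 is applied to the days in 1.3.
- *That baseline is the only scheduled rating affected.* Day 12 is printed as both an infusion day and a MADRS day. That entry has its own problem: it is also listed as a WET day, although Section 4.1 puts WET sessions and infusions on different days. The schedule needs reconciling, but Day 12 cannot simply be set aside.
- *That the sentence is leftover text.* The same paragraph calls the MADRS a "clinical predictor for Aim 3 analyses", while 9.4.9 says only "Secondary efficacy endpoint analyses and Aim 2 analyses are exploratory". But Aim 3 is also mentioned in 4.1 and in several other scale descriptions in 8.1, so its presence here says little about this sentence.

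Finally, the stakes are low. The study is a single-arm pilot of up to 15 participants with no formal hypothesis testing. Section 9.4.3 specifies a mean change with confidence interval only for the CAPS-5, and mixed models are optional. Section 9.4.1 allows unsuitable methods to be replaced before database lock. All of this holds and limits the severity. A later change of method could rescue a common-item score if item scores were kept, but not the full 10-item baseline.

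**Conclusion.** The point holds as a minor flaw in the plan as written. Taken literally, 8.1 and 1.3 together give a shortened MADRS at baseline and a full one at weeks 6 and 12, and at weeks 16, 20 and 24 under the synopsis. MADRS improvement is then understated by the baseline score on the dropped items, between 0 and 12 points.

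The direction follows from the rule alone. The upper limit of 12 rests on the assumption of one sleep and one appetite item. The typical size, and any percentage of improvement lost, cannot be stated from the documents. Nor do they show that the short form will in fact be used on Day 1; what is certain is that the plan does not say otherwise. The CAPS-5 primary endpoint does not depend on this.

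**What to change.** In 8.1, do one of two things:

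- state that the full 10-item MADRS is given at the Day 1 pre-infusion baseline and at any scheduled weekly MADRS that falls on an infusion day; or
- delete the modified-form sentence.

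If the modified form is kept at any analysed visit, retain item-level scores and compute every MADRS change, plot and model that includes that visit on the common items only.

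The cost is one sentence added or removed. In conduct it adds the sleep and appetite items at one visit (two if Day 12 stands), or only a scoring rule.
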